Este estudio es un ensayo clínico aleatorizado simple, y tendrá como objetivo: Evaluar el efecto de un programa de ejercicio físico aeróbico sobre la disminución de los triglicéridos, presión arterial, obesidad abdominal, glucosa alterada y el aumento en el HDL en estudiantes de nivel superior de la Universidad de Colima, ya que en esta población mexicana se ha presentado una alta prevalencia de obesidad, sedentarismo e inactividad física, factores que influyen en el alto riesgo para el desarrollo de los trastornos metabólicos y enfermedades cardiovasculares. Material y método: Se implementará un ensayo clínico aleatorizado simple. La muestra será de 48 estudiantes de nivel superior voluntarios de la Universidad de Colima, que estarán divididos en dos grupos de 24 personas. Instrumentos: Cuestionario IPA-Q (Anexo 6), circunferencia abdominal (anexo 7), presión arterial (anexo 8), extracción de sangre por punción venosa para el HDL, triglicéridos y glucemia (anexo 9) Queen's college step test (10). Procedimiento: Una vez se reclute y se procese toda la información de las pruebas, se tomarán en cuenta los criterios de inclusión establecidos (tabla 2) para obtener el total de la muestra. Se realizará una aleatorización simple a través de una bolsa con sobres blancos sellados que contendrán por dentro la letra al grupo que pertenece el sujeto. Cada participante sacará un sobre, escribirá su nombre encima de él y lo entregará a la persona encargada, posteriormente, estos sobres se abrirán y se asignarán los participantes a los grupos siguiendo el criterio del simple ciego, de acuerdo con la letra que tenga dentro del sobre (control n=24 y experimental n=24). El Grupo experimental realizará un programa de ejercicio físico aeróbico (EFA) que involucra trote, natación (actividades acuáticas) y bicicleta estática durante 8 semanas, tres veces por semana con una duración de 60 minutos por sesión de ejercicio a una intensidad del 57% al 76% de la frecuencia cardíaca máxima (FCM). El grupo control realizará un ejercicio físico aeróbico de caminata al 57% al 76% de la FCM. Posibles resultados: Se espera de esta intervención tener cambios favorables en los trastornos que padece la muestra de intervención y corroborar la eficiencia del ejercicio físico aeróbico planificado en disminuir estos riesgos.

Palabras claves: Ejercicio, obesidad, HDL, Triglicéridos, hipertensión.

Abstract

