This study is a simple randomized clinical trial, its **objective** is to evaluate the effect of an aerobic physical exercise program on the reduction of triglycerides, blood pressure, abdominal obesity, altered glucose levels, and the increase in HDL in college-level students at the University of Colima, due to the high prevalence of obesity, a sedentary lifestyle, and physical inactivity in Mexican population, all of which contribute to a high risk for the development of metabolic disorders and cardiovascular diseases. **Methods and Materials:** A simple randomized clinical trial will be conducted with a **sample** of 48 voluntary students from the University of Colima, divided into two groups of 24 people. **Instruments:** IPA-Q questionnaire (*Annex 6*), waist circumference (*Annex 7*), blood pressure (*Annex 8*), blood extraction by a venous puncture for HDL, triglycerides, and blood glucose (*Annex 9*), Queen's College Step Test (*Annex 10*). **Procedure:** Once all the information from the tests is collected and processed, inclusion criteria (*table 2*) will be taken into consideration to obtain the total sample. Simple randomization will be carried out through a bag of sealed envelopes that will contain the letter of the group to which the subject belongs. Each participant will draw an envelope, write their name on it and hand it to the supervisor. Afterwards, these envelopes will be opened and participants will be assigned to the groups following the simple blind criteria, according to the letter on the envelope. The Experimental Group will undergo an aerobic physical exercise (APE) program involving jogging, swimming, and static cycling, three times a week with a duration of 60 minutes per exercise session with a progressive intensity, which will start at 57%-63% of the maximum heart rate (HRmax) in the first 4 weeks of the study, and will increase to 64% -76% in the final four weeks, fulfilling the principle of progressive overload. The control group will perform aerobic physical exercise, which will be walking at 57% to 76% of HRmax. **Expected results:** This intervention will lead to favourable changes in the disorders experienced by the intervention population and, at the same time, confirm the effectiveness of the planned aerobic physical exercise in reducing these risks.

Keywords: Exercise, Obesity, HDL, Triglycerides, Hypertension.

1. Introduction

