After forming the (A) control and (B) experimental groups, they will be divided to provide them instructions for compliance with the exercise program while maintaining single-blind conditions. In the control group (A), the exercise prescription used by Habibzadeh in 2010 will be implemented: which involves walking for 30 minutes at an intensity of 57% to 76% of the maximum heart rate, three times per week (Monday, Wednesday, and Friday) for eight weeks (*annex 11*). They will always be accompanied by a previously trained physical education student (Monitoring the intensity range in which the subjects must be during the session, will be done through the effort perception scale (*Annex 12*), heart rate at 15 seconds multiplied by 4 or the H10 polar monitor) (83). On the other hand, the experimental group (B) will engage in an aerobic exercise program (jogging, aquatic activities, and stationary cycling) lasting 40 to 60 minutes, three times per week (Monday, Wednesday, and Friday) for eight weeks, always under the supervision of the principal investigator. Each participant in the experimental group will receive a structured exercise prescription tailored to their specific condition, considering the established aerobic training ranges (57% to 63% of maximum heart rate) (*annexe 11*). (Monitoring the intensity range in which the subjects must be during the session will be done through the effort perception scale (*Annex 12*), heart rate at 15 seconds multiplied by 4 or the H10 polar monitor).

By the end of the first four weeks, the second round of assessments and samples will be done, taking into consideration: Abdominal circumference (*annexe 7*), blood pressure (*annexe 8*), blood collection by venipuncture for HDL, triglycerides and glycemia (*annexe 9*), and the Queen's College step test will be performed (3 minutes) (*annexe 10*), (after completing all the tests, every participant will receive refreshments and will be asked if they are in good

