condition to conclude their assessments, if not, they will be monitored until their answer is affirmative). Subsequently, after completing sample collection and assessments, the control group (A) will continue with the same dynamics as in the initial weeks. The experimental group (B) will maintain the same exercises (jogging, aquatic activities, and stationary cycling), but their intensity may be adjusted from 64% to 76% of the maximum heart rate if favourable results are obtained from the cardiorespiratory fitness test (*annexe 11*), since this shows the level of evolution of the subject after the initial intervention and thus, the FITT-VP principle in exercise prescription would be fulfilled.

At the end of the last 4 weeks of the aerobic physical exercise program, the same sampling will be concluded; Abdominal circumference (*annexe 7*), arterial pressure (*annexe 8*), blood collection by venipuncture for HDL, triglycerides and glycemia (*annexe 9*), and the Queen's College step test will be performed (3 minutes) (*annexe 10*) (after completing all the tests, every participant will receive refreshments and will be asked if they are in good condition to conclude their assessments, if not, they will be monitored until their answer is affirmative), finishing the proposed intervention protocol.

10. Study flowchart

11. Statistical analysis

The statistical analysis will be conducted using the Statistical Package for the Social Sciences (SPSS) Statistics 26 from Business Machine (IBM). Descriptive statistics will be carried out, including measures of central tendency for the variables of age, sex and IPA-Q. Normality tests will be applied such as Kolmogorov-Smirnov for samples > 50 , and Shapiro-Wilk for samples < 50 . For the levels of triglycerides, glucose, HDL (High-Density Lipoprotein), abdominal circumference, and cardiorespiratory fitness, paired-sample T-tests will be used if the data follow a normal distribution, but if they do not, the Wilcoxon signed-rank test will be employed. To compare the control and experimental groups, independent-sample t-tests will be used if the data is normally distributed, otherwise the Mann-Whitney U test will be used. Likewise, a multivariate analysis will be carried out to relate the influence of physical exercise

on metabolic alterations. A significance level of $p \leq 0.05$ will be considered statistically significant.

12. Ethical considerations

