	Means	Day of the week	Duration	First four weeks intensity	Last four weeks intensity
Cardiorespiratory endurance	Walk	Monday	60 min	57% - 76% of HR Frequency	57% - 76% of HR Frequency
Cardiorespiratory endurance	Walk	Wednesday	60 min	57% - 76% of HR Frequency	57% - 76% of HR Frequency
Cardiorespiratory endurance	Walk	Friday	60 min	57% - 76% of HR Frequency	57% - 76% of HR Frequency

Source: Based on reference (83)

Table 12. General physical exercise prescription for the Experimental group (B).

	Means	Day of the week	Duration	First four weeks intensity	Last four weeks intensity
Cardiorespiratory endurance	Jogging	Monday	60 min	57% - 63% of HR Frequency	64% - 76% of HR Frequency
Cardiorespiratory endurance	Swimming	Wednesday	60 min	57% - 63% of HR Frequency	64% - 76% of HR Frequency
Cardiorespiratory endurance	Static Bicycle	Friday	60 min	57% - 63% of HR Frequency	64% - 76% of HR Frequency

Source: Self-made based on references (72, 114, 115)

Note: This planning will be adjusted in volume after the first 4 weeks, considering the subject's adaptations in the second test session.

Annexe 12. Borg Scale

Table 13. Modified Borg Scale

Modified Borg Scale	
0	Total rest
1	Very low effort
2	Soft
3	Moderated effort
4	A bit hard
5	Hard
6	Hard
7	Very hard
8	Very hard
9	Very hard
10	Maximal effort

Source: Self-made based on reference (116)

Annexe 13. Aerobic or Cardiorespiratory Fitness. Classification Scale. Estimated Maximum Oxygen Consumption (ml • kg-1 • min-1).

Aerobic or Cardiorespiratory Fitness. Classification Scale. Estimated Maximum Oxygen Consumption (ml • kg-1 • min-1).

Classification	Age groups (years)					
	13 - 19	20 - 29	30 - 39	40 - 49	50 - 59	Sobre 60
Men						
Very Poor	< 35.0	< 33.0	< 31.5	< 30.2	< 26.1	< 20.5
Poor	35.0-38.3	33.0-36.4	31.5-35.4	30.2-33.5	26.1-30.9	20.5-26.0
Average	38.4-45.1	36.5-42.2	35.5-40.9	33.6-38.9	31.0-35.7	26.1-32.2
Good	45.2-50.9	42.5-46.4	41.0-44.9	39.0-43.7	35.8-40.9	32.2-36.4
Excellent	51.0-55.9	46.5-52.4	45.0-49.4	43.8-48.0	41.0-45.3	36.5-44.2
Superior	> 56.0	> 52.5	> 49.5	> 48.1	> 45.4	> 44.3
Women						
Very Poor	< 25.0	< 23.6	< 22.8	< 21.0	< 20.2	< 17.5
Poor	25.0-30.9	23.6-28.9	22.8-26.9	21.0-24.4	20.2-22.7	17.5-20.1
Average	31.0-34.9	29.0-32.9	27.0-31.4	24.5-28.9	22.8-26.9	20.2-24.4
Good	35.0-38.9	33.0-36.9	31.5-35.6	29.0-32.8	27.0-31.4	24.5-30.2
Excellent	39.0-41.9	37.0-40.9	35.7-40.1	32.9-36.9	31.5-35.7	30.3-31.4
Superior	> 42.0	> 41.0	> 40.1	> 37.0	> 35.8	> 31.5

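### The experimental programme after week 4 is described in incompatible ways and session lengths conflict, so the intended contrast with control is not fixed and, on permitted intensity, can be absent or reversed

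*Combined protocol and SAP*

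**What the plan says.** **Experimental arm, weeks 1-4.** The English abstract describes a progressive intensity "which will start at 57%-63% of the maximum heart rate (HRmax) in the first 4 weeks of the study". Section 9 and Table 12 (Annexe 11) give the same 57-63%. The Spanish abstract instead gives 57-76% of HRmax for the whole eight weeks and mentions no step.

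**Experimental arm, weeks 5-8.**
- English abstract: intensity "will increase to 64% -76% in the final four weeks, fulfilling the principle of progressive overload".
- Table 12: 64-76% for the last four weeks, with no condition.
- Section 9: "their intensity may be adjusted from 64% to 76% of the maximum heart rate if favourable results are obtained" on the cardiorespiratory test.
- Note under Table 12: "This planning will be adjusted in volume after the first 4 weeks", taking account of the second test session.

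**Control arm.** Section 9 prescribes "walking for 30 minutes at an intensity of 57% to 76% of the maximum heart rate", and after the mid-point tests "the control group (A) will continue with the same dynamics as in the initial weeks". Table 11 also shows 57-76% in both periods, but with 60-minute sessions.

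**Experimental session length.** Section 9 gives 40 to 60 minutes. Both abstracts and Table 12 give 60 minutes.

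**The concern.** These statements cannot all be followed. A rise for everyone differs from a rise for some, and a change in intensity differs from a change in volume. Section 9 sets no step-test result that triggers the rise, and it does not say what happens to participants without a favourable result. Two teams working from this document could deliver different experimental programmes.

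The comparator is itself supervised aerobic exercise, so the trial estimates only the difference between two exercise prescriptions. If that difference is not fixed in advance, a null result could mean that the programme adds nothing over walking or that the arms were prescribed much the same work. A positive result could not be tied to a stated difference in intensity, duration or progression.

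**Working it through.** The plan states no figure for the intensity contrast, so the check sets the prescribed ranges against each other.

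**Inputs.** Intensity bands and minutes are those listed above. HRmax is 220 minus age (section 2.5). Three sessions a week for 8 weeks gives 3 × 8 = 24, which matches the 24 sessions in Table 4. Each four-week period has 12.

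**Step 1: ceilings in weeks 1-4 (English abstract, section 9, Annexe 11).** Control 76%, experimental 63%: 76 − 63 = 13 points. At age 20, HRmax = 220 − 20 = 200. Control is 0.57 × 200 = 114 to 0.76 × 200 = 152 beats/min. Experimental is 114 to 0.63 × 200 = 126. The gap at the ceiling is 152 − 126 = 26 beats/min. At 18 the ceilings are about 154 and 127; at 25, about 148 and 123.

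**Step 2: band midpoints (% of HRmax).**

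| Reading | Weeks 1-4 | Weeks 5-8 | Eight-week mean |
|---|---|---|---|
| Control | (57+76)/2 = 66.5 | 66.5 | 66.5 |
| Experimental, all step up | (57+63)/2 = 60 | (64+76)/2 = 70 | (60+70)/2 = 65 |
| Experimental, remains at 57-63% | 60 | 60 | 60 |
| Experimental, Spanish abstract | 66.5 | 66.5 | 66.5 |

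With step-up, experimental has the higher floor in weeks 5-8 (64 against 57) and the same ceiling. That does not quite offset weeks 1-4: control's eight-week midpoint is 1.5 points higher. Without step-up it is 6.5 points higher. Under the Spanish abstract there is no difference.

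**Step 3: crude dose over 24 sessions, as % of HRmax × minutes.** This index is used here only to bring in session length; the plan does not define it.

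Annexe 11 durations (60 minutes in both arms):
- Control: 24 × 60 × 57 = 82,080 to 24 × 60 × 76 = 109,440.
- Experimental with step-up: 12 × 60 × (57+64) = 87,120 to 12 × 60 × (63+76) = 100,080.
- Experimental without: 24 × 60 × 57 = 82,080 to 24 × 60 × 63 = 90,720.

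Section 9 durations (control 30 minutes, experimental 40-60):
- Control: 24 × 30 × 57 = 41,040 to 24 × 30 × 76 = 54,720.
- Experimental with step-up: 12 × 40 × (57+64) = 58,080 to 12 × 60 × (63+76) = 100,080.
- Experimental without: 24 × 40 × 57 = 54,720 to 24 × 60 × 63 = 90,720.

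With the Annexe 11 durations the ranges overlap and control can exceed experimental. With the section 9 durations control's maximum (54,720) only equals the experimental minimum without step-up. The volume change in the Annexe 11 note has no stated amount, so it cannot be included.

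**The case against.** A reader might infer more than the documents support, in four ways.

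**That control is the harder-exercised arm.** The texts show only that control is permitted a higher intensity. Its wide band equally allows every session at 57-63%, and with the section 9 durations its total work does not exceed the experimental arm's.

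**That control may spend 24 of 24 sessions at moderate intensity and some experimental participants none.** This sets control's most generous use of its band against the experimental arm's worst case. It also relies on Table 3, which labels 57-63% light, whereas the text of section 2.6 calls 50-59% of HRmax the moderate zone. And it assumes that participants without a favourable test stay at 57-63%, which section 9 does not say.

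**That tying intensity to the week-4 test biases the comparison.** It does not. A response-guided step is part of the assigned strategy, and comparison by randomised arm remains valid. The fault is that the trigger is undefined and that other passages contradict the condition.

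**That the trial cannot answer its question.** The objective and hypothesis concern an aerobic exercise programme, not intensity alone, and the arms also differ in type of exercise, supervision and individual tailoring.

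It can also be said that Table 12 is a general prescription, that section 9 tailors it to each participant, and that volume and intensity could change together. That softens the conflict over the volume note. It does not reconcile an automatic rise with a conditional one, the flat band in the Spanish abstract, or 30 with 60 minutes for control.

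**Conclusion.** The concern holds for the unreconciled prescription. After week 4 the experimental programme is automatic, conditional on an undefined result, a change of volume, or flat, depending on the passage. Session length conflicts in both arms.

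On permitted intensity the contrast is absent under the Spanish abstract. Under the other passages it is reversed at the ceiling in weeks 1-4, by 13 points. Over eight weeks the midpoint favours control by 1.5 points if all step up and by 6.5 points for anyone who remains at 57-63%. On crude dose, control can exceed experimental only with the Annexe 11 durations.

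These figures describe what the plan permits, not what participants will do. They rest on band midpoints and limits, on 220 minus age, and on an index the plan does not define. The passages need reconciling before the programme is delivered, because the choice among them changes the intervention being tested.

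**What to change.** Reconcile the two abstracts, section 9 and Annexe 11 (Tables 11 and 12 and the note) into one statement per arm for weeks 1-4 and for weeks 5-8. It should cover intensity, volume, session duration, and whether any change applies to all or is conditional. If conditional, state the step-test result that triggers it and what happens otherwise. Which prescription is right is for the investigators; no view is taken here.

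Record pulse and minutes at every session in both arms, and report achieved % of HRmax and minutes by arm and period beside the outcomes. Section 9 lists the effort scale, a 15-second pulse or a chest monitor as alternatives, and Table 8 budgets four monitors, so heart rate at each session is not assured as written. Making the 15-second pulse routine would close that gap. Word the conclusion to match the contrast delivered.

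The cost is protocol wording and a small recording burden, with no added visits or participants. The drawback for the sponsor is that the contrast must be set in advance and reported even if it proves small.

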There are various alternatives to measure and evaluate people's cardiovascular condition, one of the most used is: Queens College, which aims to determine aerobic capacity based on cardiorespiratory tolerance(91).

The test consists of going up and down a step for three continuous minutes, following these parameters: During the test, the same foot has to be used to go up and down, legs should fully

extend once on top of the step, and arms should be kept by the sides throughout the test, all while maintaining the correct cadence per cycle (91).

To complete one execution or cycle, you must have gone up and down the step while adhering to a metronome. For males, the metronome should be set at 96 beats per minute, and for females, it should be set at 88 beats per minute. It is important for the subject to practice the correct cadence for each completed execution or cycle: males – 24 executions per minute, and females – 22 executions per minute. After completing the test, the subject remains standing for 5 seconds, and then their pulse is taken for 15 seconds. Then, the palpated beats during those 15 seconds are then multiplied by 4(91).

The interpretation of the results is not complex, as this test is quite straightforward for those who perform it. The results can be estimated based on maximum oxygen consumption per unit of body weight. Simply find the recovery heart rate (HRrec) result in this table and read the estimated value of maximum oxygen consumption relative to weight in the next column. It's important to note that these ranges are for university students, as this population has different conditions compared to other populations (91). For a more precise estimation, the following regression equations should be used: Males: $Vo_2 \text{ max, ml x Kg}^{-1} \text{ x min}^{-1} = 111.33 - (0.42 \times \text{HRrec})$, Females: $Vo_2 \text{ max, ml x Kg}^{-1} \text{ x min}^{-1} = 65.81 - (0.1847 \times \text{HRrec})$ (Anex 11).

Similarly, there is a questionnaire known as the International Physical Activity Questionnaire (IPAQ), which, according to Palma in 2022, aims to assess an individual's level of physical activity. It collects information through questions that inquire about time spent on moderate and vigorous activities, as well as the time spent sitting or being inactive in daily life. The IPAQ consists of two forms: a lengthy one and a short one(92).

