5.2.2. Specific Objectives

1. To establish the prevalence of metabolic disorders (abdominal obesity, triglycerides, HDL, hypertension, and glucose alterations).
2. To determine and compare the post-intervention level of physical activity using the long version of the International Physical Activity Questionnaire (IPAQ).
3. To determine and compare the post-intervention level of cardiorespiratory fitness through the Queen's College Step Test.
4. Compare post-intervention prevalence levels of metabolic disorders (HDL, triglycerides, abdominal fat, hypertension, blood glucose alterations) in higher education students.
5. Determine the level of association between metabolic disorders and cardiorespiratory fitness pre- and post-intervention.

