Arterial Hypertension	Subject's systolic and diastolic blood pressure measured in mercury millimeters (mmHg)	Quantitative Continuous Ratio	It is considered an alteration when: Males > 130/85 mmHg Females > 130/85 mmHg	Sphygmomanometer
Physical Activity Level	Physical Activity performed by the subject 7 days before the survey	Qualitative Ordinal	PA: Low, Medium, High	IPA-Q (International Physical Activity Questionnaire)
Physical Fitness Test: Aerobic	Subject's cardiorespiratory capacity using an	Qualitative Ordinal	Very Poor Poor Average	Quee's College Step Test

Capacity	effort test.		Good Excellent Superior	
----------	--------------	--	-------------------------------	--

Source: self-made based on the reference (11,105).

Table 6. Independent variables

Variable	Operational definition	Nature	Scale	Instrument
Aerobic physical exercise	Individually adapted aerobic physical exercise program meeting the WHO 2021 criteria and the FITT Principles.	Quantitative Continuous Ration	57% - 76%	Prescription

Source: self-made.

Table 7. Intervinient variables

Variable	Operational definition	Nature	Scale	Instrument
Age	Chronological age in years	Quantitative Continuous	18 - 24 years	Survey
Sex	Genetically corresponding sex	Qualitative Dichotomous nominal	Male and Female	Survey

Source: self-made.

8. Location for carrying out the protocol

University of Colima's Sports Center (central campus).

9. Study Procedure

Once the project is approved by the Bioethics Committee from the Faculty of Medicine at the University of Colima (Annex 1) and the Ethics Committee from Colima's Regional Hospital (Annex 2), annexing a no-conflict of interest letter (Annex 3), letters of intent will be prepared and sent to the directors of the faculties within the central campus of the University of Colima (Annex 4). Their purpose is to inform them about the project's generalities, obtain permission to share it with the students and address any questions they may have

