Following the explanation of the performance, the subject will be allowed a 15-second practice session. The correct cadence for each completed performance or cycle must be checked. To complete a performance or cycle, the step must have been ascended and descended once, to a count of four: up-up-down-down! setting the metronome to: men - 96 beats min⁻¹ and women - 88 beats min⁻¹. The subject must practise the correct cadence for each completed performance or cycle: men - 24 performances/min, 2.5 seconds for each cycle and women - 22 performances/min, 1 second for each cycle (113).

Set the watch for the test: 3 minutes for both men and women. Activate the metronome: for men, the metronome is set at 96 beats/min, and for females it should be 88 beats/min. At the beginning of the test, the step is ascended and descended at a rate of 24 (men) and 22 (women) times per minute. After the 3-minute test has been completed, the participant remains standing for 5 seconds and immediately afterwards the pulse is taken for 15 seconds, then the beats felt during these 15 seconds are multiplied by 4 (pulse-15 sec x 4) to convert it into beats/minute. This resulting value is known as the Recovery Heart Rate (HRrecup) (113).

Percentile ranks and classification for the Queens College Step Test recovery heart rate and its estimate of maximal oxygen uptake for male and female college students.

Percentile rank	Women's heart rate frequency (Lat/min)	VO2max	Men's heart frequency (lat/min)	VO2max
-----------------	--	--------	---------------------------------	--------

Rango Percentil	FCrecup. Mujeres (lat·min ⁻¹)	VO ₂ máx (mL · kg ⁻¹ · min ⁻¹)	FCrecup. Varones (lat·min ⁻¹)	VO ₂ máx (mL · kg ⁻¹ · min ⁻¹)
100	128	42.4	120	61.0
95	140	40.0	124	59.3
90	148	38.5	128	57.6
85	152	37.7	136	54.3
80	156	37.0	140	52.6
75	158	36.6	144	50.9
70	160	36.3	148	49.2
65	162	35.9	149	48.7
60	163	35.7	152	47.5
55	164	35.5	154	46.7
50	166	35.1	156	45.9
45	168	34.8	160	44.2
40	170	34.4	160	43.4
35	171	34.2	164	42.5
30	172	34.0	166	41.7
25	176	33.3	168	40.8
20	180	32.6	172	39.2
15	182	32.2	176	37.5
10	184	31.8	178	36.6
5	196	29.6	184	34.1
0	-	-	-	-

NOTA: De: *Laboratory Experiments in Exercise Physiology*. (p. 45), por J. Magel, & W. McArdle, 1976, New York: Queens College of the City University of New York. Copyright 1976 por J. Magel, & W. McArdle.

Annexe 11. Sports planning for intervention and control groups

Table 11. General physical exercise prescription for the control group (A)

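### Sex is a declared intervening variable but enters no named test: it should be in the between-arm models and in the objective 5 associations, above all if raw VO2max is analysed

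*Combined protocol and SAP*

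**What the plan says.** Protocol section 7, Table 7, lists two intervening variables, age and sex, the latter defined as "Genetically corresponding sex". In section 11 sex appears once: "Descriptive statistics will be carried out, including measures of central tendency for the variables of age, sex and IPA-Q".

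For fitness and the metabolic measures, section 11 names a within-group test ("abdominal circumference, and cardiorespiratory fitness, paired-sample T-tests will be used if the data follow a normal distribution", otherwise Wilcoxon) and a between-group test ("To compare the control and experimental groups, independent-sample t-tests will be used if the data is normally distributed", otherwise Mann-Whitney U). It does not say whether the between-group test uses post-intervention values or change. Objective 3 speaks of comparing the level after the intervention. A further sentence begins "Likewise, a multivariate analysis will be carried out to relate the influence of physical exercise" and ends with metabolic alterations. It gives no model or covariates, and it concerns exercise rather than fitness.

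Objective 5 is to "Determine the level of association between metabolic disorders and cardiorespiratory fitness pre- and post-intervention". Section 11 names no method for it. Section 9 describes simple randomization by sealed envelope, without stratification.

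On the step test, section 2.8.5 gives a separate VO2max equation for each sex ("For a more precise estimation, the following regression equations should be used"). Annexe 10 tabulates recovery heart rate and "its estimate of maximal oxygen uptake for male and female college students". Table 5 declares aerobic capacity ordinal, Very Poor to Superior, and Annexe 13 gives separate bands for men and women.

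**The concern.** The plan recognises sex as relevant and then controls it in neither the design nor a named analysis. Estimated VO2max differs strongly by sex, partly because the conversion equations themselves differ. An unadjusted comparison of post-intervention VO2max would put that difference into the error term of a trial with 24 per arm, and simple randomization can leave the arms with unequal numbers of men.

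Objective 5 raises a separate issue. Fitness is not randomized, so a pooled association between fitness and a sex-dependent measure such as HDL can arise from sex alone. Under plausible inputs it would run in the direction of fitter students having lower HDL.

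**Working it through.** 1. **The plan's sample size.** Section 6.2: n = 6.2 × (22.53² + 12.88²) / (131.31 − 116.90)² = 6.2 × 673.5 / 207.6 = 20.1, and × 1.2 gives 24 per group. This reproduces. Section 2.4 shows that these are triglyceride figures, so the fitness comparison inherits 24 per arm without a calculation of its own.

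2. **The sex gap.** Men: 111.33 − 0.42 × HR. Women: 65.81 − 0.1847 × HR. The slope ratio is 0.42/0.1847 = 2.27. At the Annexe 10 median heart rates (156 and 166 bpm) the equations give 45.8 and 35.1, against tabulated 45.9 and 35.1. The tabulated gap is 10.8 ml/kg/min. At the same heart rate of 160 the equations alone differ by 44.13 − 36.26 = 7.9.

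3. **Share of variance.** SDs from the 85th and 15th percentiles (divisor 2 × 1.036): men (54.3 − 37.5)/2.073 = 8.10; women (37.7 − 32.2)/2.073 = 2.65. With half men, an assumption because the documents give no sex mix:
   - within-sex variance = (8.10² + 2.65²)/2 = 36.4 (SD 6.03)
   - between-sex variance = 0.25 × 10.8² = 29.2
   - total = 65.5 (SD 8.09); sex share 44%; sample-size ratio 65.5/36.4 = 1.8.

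   Over 20% to 80% men and other percentile pairs the share is 26% to 54%. Drawing heart rates from the 5th to 95th percentiles instead, which trims the tails, gives VO2max SDs of 6.3 (men) and 2.1 (women) and shares of 46%, 57% and 62% at 30%, 50% and 70% women.

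4. **Power, raw post-intervention VO2max.** Assume a 12 bpm fall in recovery heart rate, half women, SDs 6.3 and 2.1, gap 45.9 − 35.0 = 10.9. The fall is worth 0.42 × 12 = 5.04 in men and 0.1847 × 12 = 2.22 in women, mean 3.63.
   - Within-sex variance: (6.3² + 2.1²)/2 = 22.05.
   - Unadjusted: control arm 22.05 + 0.25 × 10.9² = 51.75. In the experimental arm the gap grows to 13.72, so 22.05 + 0.25 × 13.72² = 69.11. The average is 60.43 (SD 7.77), SE = 7.77 × √(2/24) = 2.24, ratio 3.63/2.24 = 1.62. Power ≈ Φ(1.62 − 2.01) = 35%; simulation gives 34%.
   - Adjusted for sex: residual variance 22.05 + ((5.04 − 2.22)/4)² = 22.55 (SD 4.75), SE 1.37, ratio 2.65. Power ≈ Φ(2.65 − 2.01) = 74%; simulation gives 74%.

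   With the wider SDs of step 3 and an assumed difference of 4 ml/kg/min, power is 40% unadjusted and 63% adjusted. For 80% power, n falls from 65 to 36 per arm.

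5. **Other scales, same 12 bpm effect.** Change scores without a sex term: 58%, 73% and 91% power at assumed pre-post correlations of 0.3, 0.5 and 0.7. Annexe 13 classes: about 70%, with sex explaining only about 2% of class variance.

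6. **Chance imbalance.** With 24 men among 48 and 24 per arm (hypergeometric), the arms differ by 4 or more men with probability 39%. A difference of 4 shifts mean VO2max by 4/24 × 10.8 = 1.8 ml/kg/min.

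7. **Objective 5 with no within-sex relation, pooled continuous measures, half men.** r = 0.25 × gap(VO2max) × gap(Y) / (SD of VO2max × SD of Y). The documents give no mean HDL or waist by sex. The sex gaps are assumed equal to the gaps in the Table 5 limits (10 mg/dl and 5 cm).
   - HDL, assumed within-sex SD 10: 0.25 × 10.8 × 10 / (8.09 × √(100 + 25)) = 0.30, negative in sign. For SDs of 6 to 14, r runs from −0.43 to −0.22. At n = 48 this reaches p ≤ 0.05 in 54% of samples (33% to 86%).
   - Waist, assumed SD 12: 0.25 × 10.8 × 5 / (8.09 × √(144 + 6.25)) = +0.14 (+0.12 to +0.26 for SDs of 14 to 6), below the roughly 0.28 needed for significance at n = 48.

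**The case against.** The strongest reply is that the declared fitness variable is already standardised for sex. Table 5 makes it ordinal, Annexe 13 has separate bands, and the Annexe 10 medians of both sexes fall in Good. On that scale the sex effect is about 2% of variance. This stands, and it limits the point. It does not close it, because section 11 assigns fitness a t-test if normally distributed, which suggests a continuous scale, and never says which scale is analysed.

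Four stronger readings are tempting and are not supported:

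- *All pooled fitness tests are swamped by sex.* The within-group test is paired, which removes the constant gap, and a change-score comparison largely does too. The 34% belongs only to raw post-intervention VO2max.
- *The arm comparison is biased.* Randomization protects it. Sex costs precision and permits chance imbalance.
- *The objective 5 results are confounded as planned.* No association method is specified, so there is no planned pooled correlation to fault. The HDL figure also rests on treating a gap in limits as a gap in means, in a sample selected for having a disorder. With fitness classes the HDL artefact shrinks to about −0.04 to −0.08.
- *Recovery heart rate must replace the declared outcome.* That is a preference. Its advantage in simulation comes from assuming an effect that is uniform in bpm.

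The unspecified multivariate analysis could include sex, but the text does not say so, and as worded it does not address objective 5.

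**Conclusion.** The point holds in a conditional form. The documents establish that sex is declared intervening, is used only descriptively, is not a stratification factor and is absent from the between-arm test.

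If raw post-intervention VO2max is compared between arms, the protocol's norms put about 26% to 62% of its variance on sex. For the assumed 12 bpm effect, adjustment raises power from about 34% to about 74%. If continuous VO2max is correlated with continuous HDL across both sexes, an association of about −0.2 to −0.4 could appear with none within either sex; the waist artefact is small.

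These sizes rest on assumptions: the sex mix, the applicability of the Annexe 10 norms to this sample, the effect size, and the HDL and waist gaps and SDs. Fitness is a secondary objective and not the basis of the sample size. For HDL and waist, adjusting the arm comparison is likewise a matter of precision. The change is worth making because it is nearly free, not because the trial's main comparison is invalid.

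**What to change.** In section 11:

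- Replace the unadjusted between-arm tests for fitness, HDL and abdominal circumference with a linear model (ANCOVA) containing arm, baseline value and sex.
- State which step-test scale is analysed: VO2max, or the Table 5 classes with the Annexe 13 bands.
- Give objective 5 a method, and estimate its associations adjusted for sex, by partial correlation or regression with sex as a term.
- Optionally add recovery heart rate, adjusted for sex and baseline, as a sensitivity analysis. It should not replace the declared outcome.

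The cost is one degree of freedom for sex and a few sentences; all the data are already collected. Part of the gain in the arm comparison of fitness comes from the baseline term alone, so the sex term matters most for objective 5 and for the unequal VO2max slopes of men and women.
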